4.2.4. Multiple Comparisons/Multiplicity

All subgroup analyses are considered exploratory for this stage of the TOGETHER trial and thus do not require adjustment for multiplicity. Treatment comparisons in focus are solely experimental versus placebo comparisons and for each treatment a matching placebo exists. Thus, all placebo comparisons can be considered approximately independent and therefore not requiring multiplicity adjustments. Lastly, multiplicity due to repeated testing is handled with Bayesian stopping rules (see section 4.3).

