4.3. Interim Analyses

Three interim efficacy analyses are planned. Assuming a uniform prior assigned to the different event rates, a total sample size of 681 patients per arm, a CER of 15%, and a RRR equals to 37.5%, we will do an interim analysis after observing 25%, 50% and 75% of the maximum number of patient outcomes, as well as at the trial completion. The posterior efficacy threshold will be 97.6% and the futility threshold will be 20%, 40% and 60%. Intervention arms(s) showing a posterior probability of efficacy crossing either boundary, will be stopped for either reason. These superiority and futility thresholds were determined based on 200,000 simulation runs in which different values of the RRR were considered (0%, 20%, and 37.5%). A description of this interim analysis in an event-based Bayesian adaptive trial and accompanying illustrating example can be found in the appendix of this document.

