APPENDIX

1. Interim analysis in an even-based Bayesian adaptive clinical trial

Suppose that we have I active treatments, such that

$$y_{ij}|p_i \sim \text{Binom}(n_{ij}, p_i), \quad i = 1, \dots, I,$$

where $j = 1, \dots, J$ denotes the number of interim analysis, n_{ij} is the number of patients randomized to the i^{th} arm, and p_i is the corresponding event rate. If we then assign a prior distribution

$$p_i \sim \text{Beta}(a, b),$$

Then by conjugation we obtain

$$p_i|y_{ij} \sim \text{Beta}(a + y_{ij}, b + n_{ij} - y_{ij}). \quad (1)$$

Control comparisons will then be based on *posterior efficacy*, namely

$$\Pr(p_i < p_{\text{ctrl}} | y_{ij}, y_{\text{ctrl}}),$$

which can be handily calculated by drawing independent Monte Carlo samples from the posterior distributions of the two arms using (1). Posterior inference on the relative risk reduction (RRR) can then be derived using the relationship

$$R_i = 1 - \frac{p_i}{p_{\text{ctrl}}}. \quad (2)$$

Proposed design for a 4-arm trial

- Perform interim analysis when 171, 342, and 513 patient outcomes have been recorded for each of the trial arms – corresponding to 25%, 50% and 75% of the maximum enrollment - and a final analysis when all 681 patient outcomes have been registered.
- Use $a = b = 1$ for beta prior distribution of all arms, corresponding to a uniform distribution.
- Stop early for efficacy if the posterior probability of efficacy exceeds 97.6%. The same test is conducted at the end of the trial if no early stopping rules are triggered.

Statistical Analysis Plan

Sponsor:	McMaster University		
Protocol:	TOGETHER trial		
Document Version No.:	1.1	Document Date:	05-May-2021

- Stop early for futility if the posterior probability of efficacy is smaller than 20% in the first analysis; 40% in the second analysis; 60% in the third analysis.

The operating characteristics of this design, as determined by 200,000 simulation runs, are as follows

Table 4: Operating Characteristics for the Proposed Bayesian Design

Arm	RRR	Power	Mean % of patients (SD)	Pr(Stop at 1)	Pr(Stop at <=2)	Pr(Stop at <=3)
1	37.50%	84.80%	64.1 (29.6)	25.20%	53.50%	73.80%
2	20%	30.70%	84.2 (26.0)	10.40%	23.90%	39.20%
3	0%	2.50%	71.1 (28.4)	16.80%	42.50%	67.00%

From Table 4 it is evident that the type I error rate of this trial design is 2.5% (one-sided). Note that a treatment with a relative risk reduction of 37.5% will – on average – require only two-thirds of the maximum sample size of 681.

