The simulation run also allows us to evaluate the frequency of the reasons for early stopping under each scenario. The details are given in Table 2 and Figure 2.

Table 5: Distribution of the Causes for Early Stopping Under Various Scenarios

[figure not shown]
RRR	Stopping Reason	Analysis 1	Analysis 2	Analysis 3	Analysis 4
0%	Early efficacy	1.00%	0.30%	0.20%	0.00%
	Futility	15.80%	23.50%	18.00%	0.00%
	None	0.00%	1.90%	6.40%	32.90%
20%	Early efficacy	6.70%	6.90%	4.90%	0.00%
	Futility	3.60%	4.70%	4.10%	0.00%
	None	0.00%	1.80%	6.30%	60.90%
37.5%	Early efficacy	24.70%	26.40%	15.30%	0.00%
	Futility	0.50%	0.20%	0.20%	0.00%
	None	0.00%	1.70%	4.90%	26.20%

Statistical Analysis Plan

Sponsor:	McMaster University		
Protocol:	TOGETHER trial		
Document Version No.:	1.1	Document Date:	05-May-2021

Figure 2: a graphical illustration of Table 2.

Example: a simulated 4-arm trial

To illustrate the application of the decision rules in the proposed design, we drew one instance of the data according to the 15% control event rate and the specified effect sizes. The resultant trial consisted of 4 analyses: three interim analyses and one final analysis. Table 3 monitors the cumulative number of events over time for each arm. Note that already at the first interim look, arm 3 was dropped due to hitting a futility rule after 171 patient outcomes were observed. Two analyses and 342 patients later, arm 1 crossed the efficacy threshold, following which no more

Statistical Analysis Plan

Sponsor:	McMaster University		
Protocol:	TOGETHER trial		
Document Version No.:	1.1	Document Date:	05-May-2021

patients were randomized to it. Arm 2 continued until all 681 patient outcomes were recorded and did not hit either decision boundary. This is illustrated in Figure 3.

An alternative form of Bayesian data monitoring is an examination of the posterior densities of the different p_i parameters ($i \in \{\text{Control}, 1, 2, 3\}$) over time as in Figure 3, starting from a uniform prior reflecting ignorance, and with centers that change over time and with reduced uncertainty, as more evidence is gathered.

Table 3 also records the proportion of patient outcomes out of the maximum number of 681 that were recorded in the trial, as well as the final decision (efficacious/non-efficacious) and a 95% interval estimate of the relative risk reduction, based on the relationship (2).

Table 6: Data and Bayesian Analysis of a Single Simulated Trial

[figure not shown]

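### The 97.6% efficacy threshold used at four analyses gives a one-sided type I error of about 6.0%, not the stated 2.5%, and Tables 4 to 6 do not follow from the written rule

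*SAP*

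**What the plan says.** Section 4.3 plans interim efficacy analyses at 25%, 50% and 75% of outcomes, and a final one: "The posterior efficacy threshold will be 97.6% and the futility threshold will be 20%, 40% and 60"%. The appendix gives the details:

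- **Looks:** "Perform interim analysis when 171, 342, and 513 patient outcomes have been recorded for each of the trial arms", then "a final analysis when all 681 patient outcomes have been registered".
- **Prior:** Beta(1,1) in every arm.
- **Efficacy:** "Stop early for efficacy if the posterior probability of efficacy exceeds 97.6"%, and for the last look "The same test is conducted at the end of the trial if no early stopping rules are triggered".
- **Futility:** posterior efficacy below 20%, 40% and 60% at looks 1 to 3.

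Table 4, from 200,000 simulation runs, reports a 2.5% rejection rate at a relative risk reduction (RRR) of 0%, 30.7% at 20% and 84.8% at 37.5%. The SAP concludes: "From Table 4 it is evident that the type I error rate of this trial design is 2.5% (one-sided"). Section 4.2.4 rests on this, saying that "multiplicity due to repeated testing is handled with Bayesian stopping rules". Section 4.1 justifies 681 per arm by 80% power at 0.05 two-sided, the counterpart of 2.5% one-sided.

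**The concern.** With flat priors and samples of this size, Pr(p_i < p_ctrl) > 97.6% is close to a one-sided test at 2.4%. One such test uses about the whole 2.5%, so four tests at the same threshold on accumulating data must exceed it. Futility stopping can remove only a little of the excess.

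The threshold decides which drugs are declared effective, and the SAP offers no other control for repeated looks. If the 2.5% is wrong, every efficacy claim from an arm carries a higher false-positive risk than readers will be told. If instead the simulation used some other rule, the SAP does not state the rule that produced its operating characteristics.

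**Working it through.** **Inputs.** Looks at n = 171, 342, 513 and 681 per arm, Beta(1,1) priors, and the efficacy and futility limits above (appendix and section 4.3). Control event rate 15%; RRR 0%, 20% and 37.5%, so treated rates of 15%, 12% and 9.375% (section 4.3). Equal allocation (section 2.2).

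**Method.** The posterior in each arm is Beta(1 + y, 1 + n − y), the appendix's equation (1). Pr(p_i < p_ctrl | data) was computed for every pair of event counts at each look. The exact joint binomial distribution of treated and control events was then carried through the four looks, removing at each look the pairs that crossed a boundary. A simulation of 2,000,000 trials agreed (5.98% under the null).

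**Reproducing Table 4.** The written rule does not reproduce it:

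| Quantity | RRR 0%: SAP / rule | RRR 20%: SAP / rule | RRR 37.5%: SAP / rule |
|---|---|---|---|
| Declared effective | 2.5% / 5.97% | 30.7% / 44.3% | 84.8% / 90.9% |
| Stopped at look 1 | 16.8% / 22.4% | 10.4% / 16.6% | 25.2% / 35.1% |
| Mean % of patients | 71.1 / 65.8 | 84.2 / 74.8 | 64.1 / 54.3 |
| Efficacy at look 1 (Table 5) | 1.0% / 2.34% | 6.7% / 11.8% | 24.7% / 34.4% |

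Under the null, efficacy by look is 2.34 + 1.59 + 1.16 + 0.88 = 5.97%.

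**Could another reading give 2.5%?**
- Ignoring futility: 6.01%.
- Control event rates from 5% to 20%: 5.85% to 6.01%.
- Jeffreys prior: 6.12%.
- Testing at 97.6% only at the final look: 2.36% to 2.39%. This is near 2.5% but contradicts the early efficacy rule.
- Simulation error: with 200,000 runs the standard error is √(0.025 × 0.975 / 200,000) ≈ 0.035 percentage points, so chance is excluded.

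Look 1 settles the matter. No arm has yet been dropped, so no later feature of the design can alter it.

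**The worked example (Table 6).** Posterior efficacy recomputed from the printed event counts:
- Arm 1, analysis 2: 28 v 45 of 342 gives 98.2%, above 97.6%. The rule stops it there; Table 6 runs it to analysis 3.
- Arm 1, analysis 3: 45 v 71 of 513 gives 99.5%; Table 6 prints 98.6%.
- Arm 3, analysis 1: 28 v 22 of 171 gives 18.1%, below 20%. The rule stops it there, and the text agrees: "Note that already at the first interim look, arm 3 was dropped due to hitting a futility rule after 171 patient outcomes were observed". Table 6 nevertheless shows 56 events at analysis 2 and 50.2% of patients.
- Arm 3, analysis 2: 56 v 45 of 342 gives 11.9%; Table 6 prints 15.9%.
- Arm 2: 56.4%, 54.5%, 64.2% and 53.2% over the four looks. Its path obeys the rule; the printed final value is 52.6%.

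**Tables 4 and 5 against each other.** Table 5 lists arms at analyses 2 and 3 with stopping reason 'None', an exit the rule does not contain. Table 4 treats them in two ways. At RRR 0%:
- Stopped by look 3, counting 'None' as stopped: 16.8 + (0.3 + 23.5 + 1.9) + (0.2 + 18.0 + 6.4) = 67.1, matching the printed 67.0 within rounding. Without 'None': 16.8 + 23.8 + 18.2 = 58.8.
- Mean % of patients, counting 'None' as fully enrolled: 16.8 × 0.251 + 23.8 × 0.502 + 18.2 × 0.753 + (1.9 + 6.4 + 32.9) × 1 = 71.1, the printed value.

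**The case against.** The type I error result itself is not open to serious dispute. The best case on the other side concerns what follows from it.

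- **Which element is wrong is unknown.** The SAP does not show whether the threshold or the tables were intended. Table 5's look 1 efficacy under the null (1.0%) fits a threshold near 99%, but its looks 2 and 3 (0.3% and 0.2%) do not: a flat 99% gives 0.71% and 0.56%. This stands. What is shown is that rule and tables disagree, and a flat 99.1% would not recreate the printed tables.
- **A flat 99.1% is only one boundary.** A boundary stricter early and about 97.85% at the end gives type I error 2.47% and power of 88.1% and 35.3% at RRR 37.5% and 20%, but with mean enrolment at RRR 37.5% of 75.8% against 64.6%. This also stands: the choice is a trade-off. It does not rescue the 97.6% rule.
- **Table 6 is a single illustrative draw.** It governs no decision, and its RRR estimates and intervals are close to correct (arm 1: 36.2% [9.9%; 55.4%] recomputed, 36.3% [9.3%; 55.9%] printed). Fair: its faults are the posterior probabilities and the stopping times of arms 1 and 3. They support the main point and are not needed for it.
- **'None' may have a meaning the SAP omits.** Possibly, but then it must be defined, and Table 4 must treat it one way.

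**Conclusion.** The stated error rate is wrong for the rule as written. The one-sided type I error is 5.97% per comparison at a 15% control event rate, about 2.4 times the stated 2.5% (5.97 / 2.5), and varies little over control event rates of 5% to 20%. Power and expected sample size are also misstated: the written rule is more powerful and stops earlier than Table 4 says, at the price of the inflated error.

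This rests on the appendix's own specification: independent Beta(1,1) posteriors, equal numbers per arm at each look, and the four looks and thresholds as listed. It makes no allowance for testing several arms. The documents cannot show whether the rule or the tables reflect the intention. Because this threshold is the SAP's only protection against repeated testing, it must be settled before the rule is used.

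**What to change.** Take one of two courses.

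1. **Keep the 2.5% and raise the threshold.** A flat 99.1% at all four analyses gives 2.40% at a 15% control event rate (about 2.3% to 2.4% over 5% to 20%). Power is 82.6% at RRR 37.5% and 29.0% at RRR 20%, still above the 80% of section 4.1. A boundary stricter at the early looks is a legitimate alternative if the sponsor prefers more power to earlier stopping; its thresholds must be listed look by look.
2. **Keep 97.6%** and restate the type I error as 6.0% one-sided, with section 4.1 amended because its 0.05 two-sided no longer applies.

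Either way, change section 4.3, section 4.2.4 and the appendix together. Regenerate Tables 4, 5 and 6 from equation (1) with a = b = 1 and the written stopping rules. Remove the 'None' exits before the final analysis, or define them, and make the text on arm 3 agree with Table 6.

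The cost is SAP wording and one simulation re-run; the maximum stays at 681 per arm. Against the printed figures, a flat 99.1% lowers power at RRR 37.5% from 84.8% to 82.6%. Against what the written rule delivers, power falls from 90.9% to 82.6%, and mean enrolment rises from 54.3% to 64.6% of the maximum at RRR 37.5% and from 74.8% to 82.4% at RRR 20%.
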